7.4. Dosage Modification

Generally, no adjustment in study drug doses (LY3298176 or placebo) will be allowed. However, if a patient is unable to tolerate a titrated dose for 2 weeks due to vomiting or moderate to severe nausea, the site should call the study CRS/CRP to discuss whether the patient should have the dose lowered to the previous dose level. Dosing of required concomitant metformin is discussed in Section 7.7.

The highest dose of Groups 1 and 2, LY3298176 15 mg, may be reduced to 12.5 mg prior to first patient visit of this study, GPGF, if the first interim analysis of the large Phase 2 study GPGB indicates that the 15 mg dose is not well tolerated. In that case, sites will be informed at the start-up meeting and in training materials. Patients will be provided dosing instructions for the 12.5 mg dose rather than the 15 mg dose.

7.5. Preparation/Handling/Storage/Accountability

The study site must store the study drug in a locked and secure environment. The study drug must be refrigerated (not frozen) at 2°C to 8°C. Dry ice should not be used for cooling. Patients will be provided with double-blinded vials containing lyophilized LY3298176 or placebo and Sterile Water for Injection (along with syringes), at clinic visits according to the Schedule of Activities (Section 2). The patients will also receive insulated bags with cooling gel packs for use in transporting the study drug from the site to the home. Study drug in each participating country will be labeled according to the country's regulatory requirements.

Commercial metformin may be made available during the treatment period to patients who entered the trial on this agent. Appropriate use and storage information will be available by referring to the package insert.

7.6. Treatment Compliance

During the study, patients will be asked to return their study drug vials and completed diaries to the site so that their compliance may be assessed.

Patients who are significantly noncompliant will be permanently discontinued from study medication. A patient will be considered significantly noncompliant if he/she misses ≥ 2 doses of study medication. Similarly, a patient will be considered significantly noncompliant if he/she is

judged by the investigator to have intentionally or repeatedly taken more or less than the prescribed amount of medication.

7.7. Concomitant Therapy

Treatment with drugs that are excluded in the entry criteria (Section 6.2) is not permitted.

The only concomitant antihyperglycemic medication permitted during this study is metformin, unless glycemic criteria for rescue therapy are met (see Section 7.8.1). Metformin treatment must be stable for at least 3 months prior to screening at a daily dose of ≥ 1000 mg/day. Patients who enter the study on diet and exercise alone will not be allowed to initiate metformin therapy after study entry unless criteria for rescue therapy are met.

Patients who are being treated with metformin upon entering this study should remain on the same (or equivalent if switching to sustained release) metformin dose throughout the course of the study unless a change in dose is required to protect patient safety.

If a patient switches from the immediate-release formulation of metformin to the sustained-release formulation, the change will be on a milligram-per-milligram basis.

In certain situations (such as during a hospitalization or perioperatively), it may be necessary for a patient to be treated with insulin(s). Treatment with insulin will be allowed for up to 14 consecutive days prior to or during the trial. If a patient requires treatment with insulin for >14 consecutive days, that patient will be considered a “rescue” patient and may remain in the study but will not receive additional study drug.

Doses of antihypertensive and lipid-lowering therapies must be stable for 30 days prior to screening. Doses of antihypertensive and lipid-lowering agents should not be changed during this study unless necessary to protect patient safety on an emergency basis (eg, hypertensive crisis).

Doses of other prescription medications (eg, thyroxine, estrogen or progesterone replacement, or selective estrogen receptor modulators) for treatment of concurrent medical conditions should remain constant during the study whenever possible.

If the need for additional concomitant medication arises, the patient may be continued in the study on study medication if, in the investigator’s opinion, the addition of the new medication does not pose a safety risk. If an additional concomitant medication is started, the sponsor should be informed as soon as possible. Nausea and/or vomiting during this study may be treated with antiemetics but should not be used prophylactically. Nonsteroidal anti-inflammatory medications (including ibuprofen, aspirin), acetaminophen, cough suppressants, antihistamines, vitamin/mineral supplements, antibiotics, and topical ointments may be used on an as-needed basis without notifying the sponsor and are not restricted by the stable dosing requirements listed above. Any additional medication used during the course of the study (including those not requiring sponsor notifications) must be documented on the appropriate electronic case report form (eCRF).

Specifically excluded concomitant medications include the following:

- Chronic use of drugs that directly reduce GI motility including but not limited to anticholinergics, antiemetics, and opiates (eg, metoclopramide, phenergan, dicyclomine, and morphine)
- Chronic use of medications that directly promote motility (eg, bethanechol and cisapride)
- Prescription or OTC medications to promote weight loss
- Systemic glucocorticoid therapy of >14 consecutive days' duration (with the exception of topical, intranasal, intraocular, intra-articular, and inhaled preparations)
- Central nervous system stimulants (eg, Ritalin-SR)
- Any drug, other than those provided in this study, that has not received regulatory approval.

7.8. Treatment after the End of the Study

7.8.1. Special Treatment Considerations (Rescue Therapy)

Investigators will be trained on how to apply decision criteria for the timing and method of intervention in patients who do not reach glycemic targets during the 12-week treatment period. An additional therapeutic intervention should be considered in patients who meet the following criteria:

- The patients are fully compliant with assigned therapeutic regimen.

AND

- In the absence of any acute condition that raises blood glucose either of the following occurs:
 - During the first 6 weeks post-randomization: An average fasting glucose level >270 mg/dL (15.0 mmol/L) occurs over at least a 2-week period (at least 3 values/week must be available).

OR

- Any time after the first 6 weeks post-randomization: An average fasting glucose level >240 mg/dL (13.3 mmol/L) occurs over at least a 2-week period (at least 4 values/week must be available).

If these conditions are met, then patients may begin treatment with another antihyperglycemic agent as determined by their physician. If treatment with another antihyperglycemic agent is instituted, then study drug should be permanently discontinued. Patients may remain in the study for safety follow-up, but the date at which they begin rescue therapy will be the last date for collection of efficacy measures.

8. Discontinuation Criteria

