Patients who develop severe, persistent hyperglycemia based on prespecified thresholds (see Section [9.2.1.2.4](#)) will receive a new glucose-lowering intervention (or rescue therapy) based on clinical judgment of the investigator, and the patient will discontinue study drug. Patients who need rescue therapy for this reason will be asked to remain in the trial until they complete all study visits for collection of safety information. Patients who discontinue study drug due to AEs will also be asked to continue in the trial for collection of safety information. Patients who are unable or unwilling to continue in the study because of an AE or any other reason will perform

an early termination (ET) visit as their final study visit. If the patient is discontinuing during an unscheduled visit, that visit should be performed as the ET visit. If the patient is discontinuing during a scheduled visit, that visit should be considered the ET visit. At this visit, patients will perform procedures listed in the Schedule of Activities (Section 2).

Study Period III (Safety Follow-Up, Visit 801):

All randomized patients who complete the treatment period will complete the safety follow-up approximately 4 weeks after their last visit on treatment.

Patients randomized to LY3298176 who have treatment-emergent anti-LY3298176 antibodies or antibodies to native GIP or GLP-1 at the last visit may be monitored after the last visit (see Section 9.9).

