10.3.3. Efficacy Analyses

10.3.3.1. Primary Analyses

The primary outcome is the difference in HbA1c change from baseline between treatment groups based on the mITT population at the planned end of the treatment period of 3 months. The primary analysis model will be a mixed model for repeated measures (MMRM) for HbA1c change from baseline to 3 months in the mITT population with treatment, visit, treatment-by-visit, baseline BMI category, and metformin use (yes, no) as fixed effects, and baseline HbA1c as a covariate. The dependent variable will be the postbaseline change from baseline values. An unstructured covariance structure will be used to model the within-patient errors. If this model fails to converge, the following covariance structures will be tested in order:

- toeplitz with heterogeneity
- autoregressive with heterogeneity, by visit
- compound symmetry with heterogeneous variances by visit
- toeplitz
- autoregressive
- compound symmetry without heterogeneous variances, by visit
- compound symmetry.

The first covariance structure that converges will be used.

The treatment p-value will be used as evidence of difference between active drug and placebo, while the comparison of least-squares (LS) means versus placebo (unadjusted for multiple comparisons) will provide magnitude and significance of this difference. The primary analysis model, MMRM, will be repeated using the PP population. If the conclusion differs from that of the mITT population, the data and analyses will be further investigated.

Descriptive statistics by treatment for HbA1c and HbA1c change from baseline at the 12-week endpoint will be presented using all observed data with no imputations and no elimination of patients with protocol violations. The descriptive statistics will be presented by visit and will include sample size, mean, SD, median, minimum, and maximum.

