10.3.3.2. Secondary Analyses

10.3.3.2.1. Analyses on Secondary Efficacy Endpoints

In addition to the primary efficacy analysis of HbA1c, the following secondary efficacy outcomes will be analyzed on the mITT population:

- Body weight change from baseline to 3 months
- Percentage of patients reaching the HbA1c target of $\leq 7.0\%$
- Change from baseline of FBG at 3 months

- Change from baseline of waist circumference at 3 months.

The secondary continuous efficacy measures (change from baseline in body weight, waist circumference, and FBG) will also be analyzed using the MMRM models described above (with censoring data collected after initiation of rescue intervention). The MMRM model will include the model terms given for the previously described primary analysis model except the baseline of the corresponding variable replacing the baseline of HbA1c, and with the addition of the HbA1c strata (<8.5% or ≥8.5%). Baseline BMI category will be dropped from the analysis models for body weight change from baseline.

The percentage of patients reaching the HbA1c target of ≤7.0% at 3 months will be analyzed using a logistic regression analysis with fixed effects of treatment and stratification factors, and baseline as a covariate.

In addition to change from baseline in weight and waist circumference, change from baseline in BMI will be listed and summarized.

Descriptive statistics for each outcome will be presented by treatment group. For continuous variables, the descriptive statistics will include sample size, LS means, LS means standard error, mean, SD, median, minimum, and maximum. For categorical variables, the descriptive statistics will include sample size, frequency, and percentage.

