6.3. Analysis Populations and Datasets

Three patient populations are defined for the analyses in this study with detailed information listed in [Table 6.1](#). Analyses datasets specifying data exclusion are listed in [Table 6.2](#).

Unless otherwise specified, listings will include FAS for all randomized patients; safety analyses, except for hypoglycemia events, will be conducted in the mITT population with the FAS; and efficacy analyses including primary and key secondary efficacy analyses will be conducted in the mITT population with the EAS.

Table 6.1. Analysis Populations

Population	Definition
All Entered	All patients who signed informed consent forms (ICFs)
All randomized (Intent-to-Treat [ITT])	All patients who were randomized to a treatment arm
Safety Population (Modified Intent-to-Treat [mITT])	All randomized patients who have taken at least 1 dose of the study medication. This is different from what is stated in the protocol. Analyses using the mITT population will be presented by the planned treatment group.

Table 6.2. Analyses Datasets

Analysis Dataset Name	Description
Full Analysis Set	All data available
Efficacy Analysis Set	Only include data on study medication without using rescue medication, i.e., excluding data after rescue medication initiation or after study treatment discontinuation (last dose date +7).

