6.8. Protocol Deviations

Important protocol deviations will be listed for all randomized patients and summarized by treatment group. A list of important protocol deviation criteria for patients from the trial issues management plan is given in [Appendix 2](#). Patients meeting criteria for important protocol deviations will be identified either by statistical programming or based off study monitoring that is maintained by the study clinical trial manager (CTM). The final list of important protocol deviations will be reviewed and documented in the Important Protocol Deviations document by the study team prior to the primary outcome DBL.

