6.9.1.1. Supporting Analyses of Primary Outcome

An MMRM analysis on the FAS will be performed for the primary parameter.

An ANCOVA model will be used on the last observation carried forward (LOCF) endpoint of HbA1c with fixed effects of metformin use, baseline BMI category, treatment, and baseline HbA1c as a covariate. Within the framework of this ANCOVA model, point estimates and 95% CIs for the mean change from baseline within each treatment group as well as for the difference in mean change from baseline between each investigative treatment group and placebo will be calculated. This analysis will be performed on FAS in addition to the EAS.

Table 6.3 describes the analyses to meet the primary objective, all performed on the HbA1c change from baseline values, including the above sensitivity analyses. The descriptive statistics will also be performed on the HbA1c measurements at each visit.

Table 6.3. Summary of Analyses for Primary Endpoint

Analysis Type	LOCF or Observed Values	Analysis Dataset ^a
MMRM ^b	Observed	EAS
MMRM	Observed	FAS
ANCOVA	LOCF	EAS
ANCOVA	LOCF	FAS

Abbreviations: ANCOVA = analysis of covariance; EAS = efficacy analysis set; FAS = full analysis set; LOCF = last observation carried forward; MMRM = mixed model repeated measures.

^a Refer to Table 6.2.

^b Primary analysis.

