15	Study Procedures	Lab Criteria	Missing HbA1c at designated visits per SoA.	Monitoring/ CLUWE/ CLO	Stats/Site Monitor/CLO	Monitoring (nonprogrammable)/ CLO and CLUWE (programmable)	Y
16	Study Procedures	Other	Missing safety data for all 3:BP, Pulse, or ECGs.	Monitoring/ InForm	Site Monitor/InForm	Monitoring (nonprogrammable)/ InForm (programmable)	N
17	Study Procedures	Other	Missing lab of lipase, amylase, LFTs, or FBG.	CLUWE	CLO	Programmable	N
18	Study Procedures	Other	Missing body wt. and/or waist circ. per SoA.	Monitoring/ InForm	Site Monitor/InForm	Monitoring (nonprogrammable)/ InForm (programmable)	N
19	Investigational product	Other	IP lost or stolen	Monitoring	Site Monitor	Nonprogrammable	Y
20	Investigational	Dosing	NA	Monitoring/	Site Monitor/InForm	Monitoring	N

	Important Protocol Deviation			Source of Information	Function Accountable for Identifying Deviation	Programmable/ Nonprogrammable	Immediate Notification (Y/N)
	Category	Sub-category	Trial-specific Term				
	product	Error		InForm		(nonprogrammable)/ InForm (programmable)	
21	Investigational product	Compliance	Missing 2 or more doses.	Monitoring/ InForm/ CLUWE	Site Monitor/InForm/ CLUWE	Monitoring (nonprogrammable)/ InForm and CLUWE (programmable)	Y

Abbreviations: BMI = body mass index; BP = blood pressure; circ. = circumference; CLO = Clinical Laboratory Operations; CLUWE = Clinical Users Working Environment; conmeds = concomitant medications; ECGs = electrocardiograms; FBG = fasting blood glucose; HbA1c = glycated hemoglobin; hrs. = hours; IP = investigational product; lab = laboratory; LFTs = liver function tests; N = no; NA = not applicable; OAMs = oral antihyperglycemic medications; SoA = Schedule of Events; T2DM = type 2 diabetes mellitus; tx = treatment; wt. = weight; Y = yes.

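### Protocol 7.7 and 8.1.1 give incompatible rules for 8 to 14-day insulin courses, and 7.8.1 leaves post-rescue HbA1c in the full analysis set dependent on which text a site follows

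*Protocol*

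**What the plan says.** **Insulin.** Protocol 7.7 accepts that insulin may be needed, for example in hospital or around surgery, and allows it for as long as 14 days in a row. Only a longer course makes the patient a rescue patient who gets no more study drug. Protocol 8.1.1 lists, as a ground for permanent discontinuation, a need for more than one week of another agent shown to work in diabetes. It applies for any reason and has no insulin exception. Breach of the discontinuation criteria is item 12 in SAP Appendix 2, with immediate notification.

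**Rescue.** Protocol 7.8.1 states that "the date at which they begin rescue therapy will be the last date for collection of efficacy measures". Protocol 5.1 says that these patients "will be asked to remain in the trial until they complete all study visits for collection of safety information".

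**Analysis.** The primary MMRM uses the EAS, which SAP Table 6.2 defines as "excluding data after rescue medication initiation or after study treatment discontinuation (last dose date +7"). The FAS is all available data. SAP 6.9.1.1 adds an MMRM on the FAS and an LOCF ANCOVA, of which it says "This analysis will be performed on FAS in addition to the EAS". Protocol 10.3.3.1 promises descriptive HbA1c statistics that "will be presented using all observed data with no imputations and no elimination of patients with protocol violations". SAP Appendix 2 item 15 counts as an important deviation "Missing HbA1c at designated visits per SoA", with no exemption for rescue. For weight, waist and FBG only, Protocol 10.3.3.2.1 specifies MMRM "with censoring data collected after initiation of rescue intervention".

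**The concern.** The insulin rules are the stronger part. Two sites with identical patients can act in opposite ways, each following a section of the protocol, and the choice decides whether Week 12 HbA1c stays in the primary data set. SAP Table 6.2 does not settle it, because it does not define rescue medication. SAP 6.7 links rescue to severe, persistent hyperglycemia, whereas Protocol 7.7 also counts insulin beyond 14 days.

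The rescue clause matters for the supporting analyses. If efficacy collection stops at rescue, the FAS holds no later HbA1c for glucose-rescued patients. A reader who sees the FAS and EAS agree could take that as reassurance about excluding post-rescue values, which it would not be. If some sites continue collection and others do not, FAS content varies by site. A site that follows 7.8.1 also triggers deviation 15.

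**Working it through.** **Inputs.** HbA1c at Visits 6, 8 and 10 (Days 28, 56, 84) and at Visit 801 (Day 105), from Protocol Table GPGF.1. Weekly doses on Days 0, 7, ..., 77, from Tables GPGF.1 and GPGF.3. EAS end after stopping drug: last dose + 7 days, from SAP Table 6.2. SD 1.1, 20 completers per arm, 13% dropout and changes of -0.2, -1.4, -1.5 and -1.5, from Protocol 10.1. All days below are nominal.

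**Step 1: the plan's own figures.** SE of a difference = 1.1 × √(2/20) = 0.348. Power = Φ(δ/SE − z).

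| δ | One-sided 0.1 (protocol) | Two-sided 0.05 (SAP) |
|---|---|---|
| 1.2 | 98.5% | 93.2% (91.9% by noncentral t, 38 df) |
| 1.3 | 99.3% | 96.2% (95.4% by noncentral t) |

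20/0.87 = 23 per arm, and 4 × 23 = 92. The stated power and sample size reproduce under either alpha and are not in dispute.

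**Step 2: insulin.** Let a course of 8 to 14 days start on Day s. Assume that a site following 8.1.1 stops drug on the 8th day of insulin, Day s + 7. The last dose is then the latest dosing day before s + 7, and the EAS ends 7 days after that dose.

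- s = 14: stop Day 21, last dose Day 14, EAS end Day 21. Days 28, 56 and 84 drop.
- s = 15: stop Day 22, last dose Day 21, EAS end Day 28. Days 56 and 84 drop.
- s = 43: stop Day 50, last dose Day 49, EAS end Day 56. Day 84 drops.
- s = 70: stop Day 77, last dose Day 70, EAS end Day 77. Day 84 drops.
- s = 71: stop Day 78, last dose Day 77, EAS end Day 84. None drops.

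| Course starts | Treatment-period HbA1c dropped under 8.1.1 | Dropped under 7.7 |
|---|---|---|
| Days 1-14 | 3 | 0 |
| Days 15-42 | 2 | 0 |
| Days 43-70 | 1 | 0 |
| Day 71 or later | 0 | 0 |

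Week 12 is among the dropped values for every start on Days 1-70.

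**Step 3: glucose rescue.** The criterion needs an average over at least 2 weeks, so the earliest rescue is about Day 14. Under 7.8.1, values after the rescue date are not collected.

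| Rescue on | Treatment-period values lost | Visit 801 value | Treatment-period values held in FAS and in EAS | Held in FAS if collection continued |
|---|---|---|---|---|
| Days 14-27 | 3 | lost | 0 and 0 | 3 |
| Days 28-55 | 2 | lost | 1 and 1 | 3 |
| Days 56-83 | 1 | lost | 2 and 2 | 3 |

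**Step 4: scale.** The documents give no rescue rate, so the effect on the supporting analyses cannot be computed. For scale, consider a 1-point HbA1c difference in one patient:

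- n = 23: 1/23 = 0.043; SE = 1.1 × √(2/23) = 0.324; 0.043/0.324 = 0.13 SE.
- n = 20: 1/20 = 0.05; 0.05/0.348 = 0.14 SE.

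As an assumed range, let 1 to 4 of 23 placebo patients be rescued, with unseen Week 12 values 0.5 to 1.5 points from what the model implies. The placebo mean in the FAS then moves by 1/23 × 0.5 = 0.02 to 4/23 × 1.5 = 0.26 points, against assumed differences of 1.2 to 1.3.

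**The case against.** On insulin, 7.7 is the specific rule and might be taken to override the general one. SAP deviation 13 supports that view, since its 7-day limit concerns oral agents and not insulin. A patient in hospital for 8 to 14 days may also miss 2 or more doses and be discontinued on that ground. These points reduce the number of patients affected. They do not remove the conflict, because 8.1.1 says that the reason does not matter and neither section gives precedence to the other.

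On rescue, ending efficacy collection is a choice open to a sponsor. Protocol 10.3.1 censors efficacy at rescue in the mITT analyses, which agrees with 7.8.1. The EAS exclusion is a filter that works whether or not later data exist. Protocol 10.3.3.2.1 does not cover HbA1c. Deviation 15 is generic, and under SAP 6.8 "The final list of important protocol deviations will be reviewed and documented" by the study team before the primary database lock. All of this stands.

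A reader might infer that post-rescue HbA1c is certain to be lost. The documents do not support that. Protocol 8.1.1 sends discontinued patients to Section 9.4, where 9.4.3 calls for the Protocol Appendix 2 tests on schedule, and that list includes HbA1c. Protocol 8.1.2 also lets patients off drug undergo all procedures, though it is permissive and sits under temporary discontinuation. So HbA1c may still be drawn as part of safety follow-up. This makes the defect one of inconsistency: what the FAS contains depends on the text a site follows.

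A reader might also infer that the primary result is biased by the rescue clause, or that the FAS analyses are worthless. Neither follows. The EAS excludes post-rescue values in any case. The FAS still tests the exclusion of data after drug discontinuation without rescue, and the LOCF ANCOVA on the EAS still varies the missing-data assumption.

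**Conclusion.** Both inconsistencies are in current text, and the SAP revision history resolves neither.

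The insulin conflict reaches the primary analysis. One to three treatment-period HbA1c values, always including Week 12, leave the EAS or stay in it according to the section a site applies, for any 8 to 14-day course starting on Days 1-70. This assumes nominal visit and dose days and drug stopped on the 8th day of insulin. Few patients should be affected.

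The rescue clause does not affect the primary EAS result for glucose-rescued patients or the stated power. Its consequence is that, where 7.8.1 is followed, FAS/EAS agreement carries no information about excluding post-rescue values, and the all-observed-data summary lacks them too. The numerical effect is unknown without a rescue rate. Nothing here indicates a reversal of the trial's conclusion.

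**What to change.** 1. Add to Protocol 8.1.1 an exception for insulin of up to 14 consecutive days under 7.7, or have the clinical team set one limit for both sections. Define the rescue start date in SAP Table 6.2 to match, and state whether, for insulin beyond the limit, it is the first day of the course.
2. Replace the 7.8.1 clause so that scheduled HbA1c, FBG, weight and waist continue after rescue, at visits that 5.1 already asks patients to attend. Align the stated purpose of those visits in 5.1. The EAS excludes these values and the FAS uses them.
3. If the sponsor keeps 7.8.1, exempt rescued patients from SAP deviation 15 and state in SAP 6.9.1.1 that the FAS does not test the post-rescue exclusion.

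Items 1 and 2 cost a short protocol amendment, site notice and retraining, one SAP definition and a few extra measurements in rescued patients. Item 3 needs SAP edits only, but it leaves the post-rescue values uncollected wherever 7.8.1 is followed.
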